**Study Product:** **Ferric Carboxymaltose (Injectafer) marketed by American Regent Inc. (Shirley NY)**

**Protocol Number:** **s17-00444**

**IND Number:** **IND Exemption Letter Requested**

## Study Summary

Title	Ferric Carboxymaltose To Improve Skeletal Muscle Metabolism in Heart Failure Patients with Functional Iron Deficiency
Short Title	FCM To Improve Sk. Muscle Metabolism in HF Patients with Fe Def.
Protocol Number	NYULMC IRB number: s17-00444
Phase	Phase 2 study of FDA-approved drug
Methodology	Double-blind, placebo-controlled single center randomized clinical trial
Study Duration	2 years
Study Center(s)	Single Center (NYULMC)
Objectives	To compare the effects of ferric carboxymaltose vs. placebo on skeletal muscle mitochondrial oxidative capacity, submaximal exercise tolerance, and health-related quality of life in HF patients with functional iron deficiency.
Number of Subjects	50 subjects will enrolled to identify 32 subjects eligible for randomization
Diagnosis and Main Inclusion Criteria	Clinically stable ambulatory chronic heart failure patients with functional iron deficiency without contraindication to study procedures (MRI and intravenous infusion of ferric carboxymaltose)
Study Product, Dose, Route, Regimen	Ferric carboxymaltose (Injectafer®) 750 mg intravenously, or normal saline (placebo)
Duration of administration	A single dose of ferric carboxymaltose or placebo will be administered.
Reference therapy	Placebo
Statistical Methodology	The change in the primary and secondary endpoints from baseline to week 4 will be compared between the two treatment arms by two-sided two sample t-test or Wilcoxon rank sum test. Significance will be decided at alpha=0.05.

[figure not shown]

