## STUDY DESIGN

The proposed study design is a prospective, single-center, randomized, double-blind, parallel group placebo-controlled study (Figure 2). Primary and secondary endpoints will be assessed before and 4 weeks after administration of ferric carboxymaltose or placebo. It is anticipated that the study will require 2 years to complete enrollment.

**Study population:** Up to 50 subjects will be recruited from the clinical practice of the NYU Advanced Cardiac Therapeutics group at NYU Langone Medical Center. 36 eligible subjects will be randomized. Study entry criteria are listed in the Human Subjects section below.

**Study visits:** The study will require 3 visits over approximately 8-10 weeks for each subject: Visit 1: Screening; Visit 2: Baseline primary and secondary endpoint measurements, randomization, and study drug administration; Visit 3: final assessment of primary and secondary endpoint measurements. Additional details of the procedures at each study visit are described below.

**Study agent and control description:** Ferric Carboxymaltose (Injectafer®, 750 mg iron/15 ml sterile single use vial) will be provided by the American Regent pharmaceuticals (Shirley, NY) to the NYU Investigational Pharmacy and stored in the NYU Investigational pharmacy at 20°C to 25°C according to manufacturer instructions. An IND exemption will be requested from the FDA. Ferric carboxymaltose is nonionic polynuclear iron (III) hydroxide carbohydrate complex that binds iron tightly and requires macrophage processing for release of iron into body stores. Ferric carboxymaltose has been demonstrated to be safe and effective in the treatment of iron deficiency anemia and is FDA-approved for treatment of iron deficiency in adult patients. The most common adverse reactions recorded in clinical trials (>2%) are nausea, hypertension, flushing, hypophosphatemia, and dizziness. The dosing and route of administration used in this study protocol are consistent with the FDA-approved prescribing information for this drug (see appendix for FDA-approved package insert) and prior studies of this agent in heart failure populations.

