**Medical History:** The following information will be obtained from review of the medical record and/or patient interview at Visit 1: 1) Left ventricular ejection fraction (date and imaging mode); 2) Etiology of heart failure (ischemic or non-ischemic); 3) Duration of heart failure (years); 4) NYHA Class (I-IV); 5) Co-morbid diseases (hypertension, hyperlipidemia, coronary artery disease, chronic kidney disease, chronic lung disease, atrial fibrillation); 6) Medications by pharmacological class: angiotensin converting enzyme inhibitors, angiotensin receptor blockers, beta-adrenergic receptor blockers, digitalis glycosides, loop diuretics, mineralocorticoid receptor antagonists, statins, aspirin, thienopyridines, warfarin, and novel oral anticoagulant agents; 7) Demographic information including age, sex, ethnicity; 8) Contact information including home, work and mobile phones, street address, email address (to be purged after completion of study visits).

**Heart Failure Symptoms:** The following information will be obtained from review of medical record and/or patient interview: 1) Functional capacity; 2) Orthopnea, paroxysmal nocturnal dyspnea, edema; 3) Medical resource use (doctor visit, emergency department visit, hospitalization); 4) Medication change; and 5) Use of appropriate measures to protect against pregnancy in women of childbearing potential.

**Cardiovascular examination:** Limited physical examination to assess evidence of congestion including assessment of jugular venous pressure, lung exam, cardiac exam, abdominal exam for hepatomegaly, and extremity exam for edema and perfusion.

**Safety Blood Monitoring:** Venous blood will be collected from a forearm vein with standard sterile venipuncture technique for analysis of biomarkers of iron stores (serum iron, total iron binding capacity, serum ferritin), complete blood count, comprehensive metabolic panel, serum phosphate, and beta-HCG (for women of childbearing potential) according to the schedule of assessments (Table 1). All laboratory analyses will be performed by the New York State licensed CLIA-compliant NYU Langone Medical Center Tisch Hospital Clinical Laboratory.

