**Adverse Event Monitoring:** The Principal Investigator is responsible for monitoring and reporting adverse events to the ethical review board. The definitions and procedures for classification and reporting of adverse events (AEs) are described in the Human Subjects section below. Subjects will be prompted to report any new problems or events since the start of the study at each visit.

**Early Withdrawal Criteria:** Subjects may be removed from participation based on the following criteria: subject request, intolerance of study drug or study procedures, intercurrent illness that alters risk of participation or interferes with study procedures, acquisition of new information that affects subject eligibility (e.g. pregnancy or prohibited concomitant medication), or other situations that would put the subject at increased risk, compromise adherence to study procedures, or confound interpretation of the study findings. Women of childbearing potential will be instructed to use accepted methods of contraception to avoid pregnancy during the study, and will have a blood pregnancy test at screening, and before all study visits with efficacy endpoint assessments.

**Early study termination criteria:** The study may be prematurely terminated or suspended by the Principal Investigator due to issues related to participant safety, study futility, failure to meet accrual, site performance, or data quality and completeness milestones, failure to adhere to ethical standards in the conduct of human subjects research, or other study protocol deviations.

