### Description of analysis sets:

Efficacy analysis dataset. Intention to treat (ITT) will be defined as all patients who have been randomized to study treatment and completed at least one follow-up visit with primary endpoint data collection. The ITT data set will be used for the primary and secondary efficacy endpoints and ancillary study endpoints.

Safety analysis dataset. All patients who received study drug, and for whom post-dose data are available, will be included in the safety analysis set.

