### c. Potential Risks

The risks of the research procedures in this protocol are generally similar to the risks of the same procedures performed in the course of clinical care. The potential risks to study participants are as follows;

**Risk of ferric carboxymaltose (Injectafer®):** Ferric Carboxymaltose (Injectafer®, 750 mg iron/15 ml single use vial) has been demonstrated to be safe and effective in the treatment of iron deficiency anemia and is FDA-approved for treatment of iron deficiency in adult patients. The most common adverse reactions recorded in clinical trials (>2%) are nausea, hypertension, flushing, hypophosphatemia, and dizziness. Rare occurrences of anaphylactic or anaphylactoid reactions have also been reported. The dosing and route of administration used in this study are consistent with the FDA-approved prescribing information for this drug. In the FAIR-HF study, ferric carboxymaltose was administered repeatedly over 6 months to 304 subjects with chronic heart failure. Reported adverse events did not differ from placebo. There were no anaphylaxis events or other allergic reaction events reported. In the CONFIRM-HF study, 150 heart failure subjects received intravenous ferric carboxymaltose for 1 year. Overall adverse events did not differ from placebo. There were no anaphylaxis events, but there was one episode of rash, one episode of urticaria, and one episode of flushing reported in the ferric carboxymaltose group. Taken together, this reported experience of repeated dosing of ferric carboxymaltose over 6-12 months in a combined group of 454 patients with heart failure does not suggest a signal of increased risk of adverse effects in heart failure when compared to clinical trial population data included in the package label.

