## Data Handling and Record Keeping

**Confidentiality:** A random Study ID code will be assigned to each participant. This code will be used on all written and electronic research records. The Principal Investigator and study coordinator will be able to link the Study ID code back to the personal information during the interval of active participation in the study, but this link will be destroyed after the subject has completed the study procedures. Consent forms, links between Study ID and personal information, case report forms, laboratory reports, and results of the 6 minute walking test, and the 31P-MRS and MRI analysis of skeletal muscle bioenergetics in response to plantar flexion exercise will be kept in a project notebook in a locked cabinet in a locked office. Research data without identifiers will be maintained

on the NYULMC REDCap system. The REDCap system provides secure password protected storage of research information behind the NYU firewall and provides quality control and audit trail functions to validate the integrity and quality of the research data.

**Confidentiality and HIPAA:** Information about study subjects will be kept confidential and managed according to the requirements of the Health Insurance Portability and Accountability Act of 1996 (HIPAA). Those regulations require a signed subject authorization informing the subject of the following:

- What protected health information (PHI) will be collected from subjects in this study
- Who will have access to that information and why
- Who will use or disclose that information
- The rights of a research subject to revoke their authorization for use of their PHI.

In the event that a subject revokes authorization to collect or use PHI, the investigator, by regulation, retains the ability to use all information collected prior to the revocation of subject authorization. For subjects that have revoked authorization to collect or use PHI, attempts should be made to obtain permission to collect at least vital status (i.e. that the subject is alive) at the end of their scheduled study period.

**Source Documents:** Source data for the current proposal will include nursing records from the CTSI, case report forms, laboratory reports, and MRI reports. These data will be kept in a project notebook in a locked cabinet in a locked room.

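### Dosed subjects who are removed early have no stated safety follow-up, and the safety set rests on undefined post-dose data rather than on exposure

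*Combined protocol and SAP*

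**What the plan says.** **Safety set** (Description of analysis sets): "All patients who received study drug, and for whom post-dose data are available, will be included in the safety analysis set". Post-dose data is not defined.

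**Exposure** (Study Summary): "A single dose of ferric carboxymaltose or placebo will be administered".

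**Removal** (Early Withdrawal Criteria): "Subjects may be removed from participation based on the following criteria: subject request, intolerance of study drug or study procedures", followed by further reasons. The text speaks of participation, not of treatment.

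**AE collection** (Adverse Event Monitoring): "Subjects will be prompted to report any new problems or events since the start of the study at each visit". Table 1 marks AE monitoring at Visit 2, the dosing visit, and at Visit 3.

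**Visits** (Study Design): there are three, and the last is described as "Visit 3: final assessment of primary and secondary endpoint measurements". No early-termination visit is listed.

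**Phosphate:** it is measured at screening and again in the safety blood panel, which is drawn according to Table 1. Table 1 marks that panel once, under Visit 3. A low value at screening is an exclusion criterion. The Potential Risks section states: "The most common adverse reactions recorded in clinical trials (>2%) are nausea, hypertension, flushing, hypophosphatemia, and dizziness".

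**Follow-up outside the visits:** the plan describes pregnancy follow-up (Risks of MRI) and, after revoked authorization, that "attempts should be made to obtain permission to collect at least vital status" (Confidentiality and HIPAA). No other is described.

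**The concern.** With a single dose, removal after the infusion prevents no further exposure. What it can end is observation. Intolerance of study drug is one of the named reasons for removal, so some of the subjects lost to later safety assessment may be those who reacted to the infusion.

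Two separate problems follow.

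- **Missing data.** AEs that appear after the dosing day, and post-dose phosphate, are collected only at Visit 3. The plan does not say whether a removed subject is still asked to attend, or is contacted in another way.
- **Set definition.** Membership of the safety set depends on what was later recorded, not on having been dosed. Because the condition is undefined, two analysts could build different sets from the same database.

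With about 16 subjects per arm, each untested subject is worth 1/16 = 6.3 percentage points. A few such losses can blur any statement about delayed reactions. The section on protections against risk also counts active surveillance for drug effects among the safeguards, and no written procedure provides it after removal.

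**Working it through.** **Inputs.** 32 randomised 1:1, so 16 per arm (Study Objectives). Dropout 0-20%, power 0.90, two-sided alpha 0.05 (Sample size calculation). Table 2 shows 16 and 13 per group at 4 weeks, with detectable differences of 1.15 and 1.3 SD.

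**Step 1: the plan's own figures.** Normal approximation, n per group = 2(1.960 + 1.282)² / d².
- d = 1.15: 21.02 / 1.3225 = 15.9, so 16.
- d = 1.3: 21.02 / 1.69 = 12.4, so 13.
- Dropout: 16 × 0.8 = 12.8, rounded to 13.

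Table 2 reproduces. At its upper dropout value the plan allows for 16 − 13 = 3 subjects per arm without week-4 data. I take these three as having no Visit 3 phosphate. This is an assumption, because Table 2 concerns the primary endpoint.

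**Step 2: what the untested could hide.** With x low phosphate results among 13 tested and 3 untested, the count among all 16 dosed lies between x and x + 3.

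| Observed | Reported rate | Possible among 16 dosed |
|---|---|---|
| 0/13 | 0% (95% Clopper-Pearson 0-24.7%) | 0/16 to 3/16 (0-18.8%) |
| 1/13 | 7.7% | 1/16 to 4/16 (6.3-25.0%) |
| 2/13 | 15.4% | 2/16 to 5/16 (12.5-31.3%) |

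The width is 3/16 = 18.8 points. It is 1/16 = 6.3 points with one untested, 2/16 = 12.5 with two, and zero with none.

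**Step 3: sensitivity to the number randomised.** The Study Design section gives 36 instead of 32, or 18 per arm. Then 18 × 0.2 = 3.6, so about 4 are untested, and 0/14 observed is compatible with 0/18 to 4/18 (0-22.2%).

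**Step 4: chance of seeing at least one event,** 1 − (1 − p)ⁿ. The rates p are assumptions; the plan gives only >2% for the common reactions.
- p = 10%: 0.815 with n = 16, 0.746 with n = 13.
- p = 5%: 0.560 with n = 16, 0.487 with n = 13.

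**Step 5: what each remedy can do.** Changing the set definition alone adds no laboratory result. In the 2/13 row, putting all 16 dosed in the denominator gives 2/16 = 12.5%, the bottom of the possible range. The missing values have to be collected, or shown as missing.

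**Step 6: carrying values forward.** Missing Data Consideration applies last value carried forward in principle and does not mention safety data. If it were applied to phosphate, the carried value would be the pre-dose one. By eligibility that value is not low, so the reported rate would always sit at the bottom of the range in Step 2.

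**The case against.** The strongest reply is that a subject who reacts on the infusion day is not lost. AE monitoring is marked at Visit 2, an unblinded nurse gives the infusion, and a physician safety monitor is available. On a plain reading the reaction is itself post-dose data, so that subject stays in the safety set with an event. This stands, and the set rule alone may exclude few people.

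A reader might infer that safety rates are biased downward, and more so in the iron arm. The documents do not support this. The person most exposed to exclusion has nothing recorded after dosing, and leaving out event-free subjects raises AE rates. Nothing in the plan links infusion intolerance to later low phosphate.

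A reader might also see a contradiction with the vital-status rule. There is none. That rule covers revoked authorization, where fresh permission is needed, and a subject removed by the investigator has revoked nothing. Nor does the plan rank phosphate above other safety results; its stated endpoints are efficacy and laboratory markers.

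It is also fair that no sentence ends safety collection at removal, that removal is discretionary, and that the investigator remains responsible for AE monitoring. The plan is silent rather than explicit. But the Sources of Materials section limits access to private health information, and use of the link from study ID to person, to active participation. This makes continued follow-up after removal harder to read into the text.

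Finally, 20% is the top of a planning range, and the plan expects few missing data. That limits the size of the problem but leaves the gap in the text.

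**Conclusion.** The concern holds as a minor point. Followed as written, the plan has no provision for collecting delayed AEs and post-dose phosphate from dosed subjects who are removed before Visit 3, and intolerance is one of the reasons for removal. Separately, the safety set is conditioned on an undefined availability of data instead of on exposure.

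At the upper end of the plan's dropout range the uncertainty is up to 18.8 percentage points per arm (22.2 if 36 are randomised), and it falls to zero if nobody is lost.

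This rests on three assumptions: that removal ends scheduled visits, that subjects without week-4 data also lack the safety blood, and that Table 1 places that blood only at Visit 3. The size is a bound on what could be hidden, not an estimate of bias, and its direction is not established.

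**What to change.** 1. In Description of analysis sets, define the safety set as all subjects who received any amount of study agent, analysed by treatment received. Delete the condition on post-dose data.
2. Reconcile Table 1, Early Withdrawal Criteria and the safety set definition. State that dosed subjects who are removed but have not refused contact still have the already scheduled Visit 3 AE inquiry and safety blood collected as data, or an AE inquiry by telephone if they do not attend. The grounds for removal are unchanged. Align the text on access to identifiers so that this contact is permitted.
3. Report laboratory abnormality rates over the number tested, beside the number dosed, by arm. State that a pre-dose phosphate is not carried forward.
4. Reconcile the 32 and 36 randomised, since this sets the denominator.

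The cost is protocol wording and a few extra contacts. The visit and the blood test are already in the schedule.

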### Analysis plan for primary and secondary endpoints:

The objective is to compare the change in the primary and secondary endpoints over time between the two treatment groups.

Descriptive analysis techniques will be used to characterize study participants. Center and variability of continuous variables will be presented as means (SD) when they follow a normal distribution and as medians and interquartile range otherwise. Log transformation will be applied on variables with skewed distribution.

The primary endpoint is change in the phosphocreatine recovery time (s). Secondary endpoints are 1) change in six-minute walk distance (m), change in quality of life score (points), and change in hemoglobin (g/dL), serum ferritin (ng/ml), and transferrin saturation (%). The change in the primary and secondary endpoints from baseline to week 4 will be compared between the two treatment arms by two-sided two sample t-test or Wilcoxon rank sum test. Significance will be decided at alpha=0.05.

We will also construct multivariable regression models with treatment assignment as the main predictor and the change in the primary or secondary endpoint as the outcome variable while adjusting for patients' characteristics such as baseline value of the endpoint, age, sex, ethnicity, hemoglobin level, and measures of disease severity and their interactions with the treatment assignment if necessary. Pre-specified subgroup analyses are based on median age, sex, heart failure etiology (ischemic vs. non-ischemic), NYHA functional Class, median serum ferritin level, and sex-stratified median hemoglobin level.

**Missing Data Consideration:** We anticipate a low percentage of missing data due to the short duration of the study and relatively small data set. The missing data will be handled by intent-to-treat analysis in principle, with last value carried forward. We will compare baseline data in subjects with and without missing data to identify factors contributing to missingness. As sensitivity analyses, a "per protocol" analysis, and analysis with multiple imputation will be undertaken with five imputed datasets using the NORM software. Parameter estimates and their standard errors will be derived by averaging across the five imputations and by adjusting for their variance.

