### 4.14: Sample size calculation:

Our pilot data demonstrated that the post-exercise phosphocreatine recovery time constant decreased by >10 seconds in all 3 non-anemic HF subjects with functional iron deficiency who received ferric carboxymaltose with mean $\pm$ SD decrease  $11.4\pm3.4$  seconds. Table 2 presents the minimal detectable difference between treatment groups over time based on estimates of a range of standard deviations of the between-group

difference and assuming 0-20% dropout, power=0.90, two-tailed alpha=0.05. Table 2 indicates that the proposed sample size provides adequate power to detect moderate to large changes in the post-exercise phosphocreatine recovery time, even when accounting for 20% drop-out. A 10-second change in phosphocreatine recovery time is likely meaningful, since our pilot data suggest that a 10-second decrease would place many HF subjects back to the normal or near normal range. The sample size of 16 subjects per treatment arm will provide >80% power to detect a 35 m difference in six minute walk distance (consistent with a moderate improvement in submaximal exercise capacity, based on data from FAIR-HF and other assumptions as above) and a 20-point difference in the KCCQ score (consistent with a large improvement in health status, based on previous data from FAIR-HF and other assumptions as above).

Table 2. Estimates of minimal detectable between-group difference for post-exercise phosphocreatine recovery time based on power 0.9 with 2-tailed alpha=0.05.

Drop-out Rate	N/group at 4 weeks	Detectable Difference (proportion of SD)	Estimated SD of between group difference (seconds)	Minimal Detectable Difference (seconds)
0%	16	1.15	2	2.3
			4	4.6
			6	6.9
			8	9.2
20%	13	1.3	2	2.6
			4	5.2
			6	7.8
			8	10.4

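### The primary test is left as t-test or Wilcoxon on change with no rule for choosing; one named baseline-adjusted ANCOVA would cost one degree of freedom and usually gain power

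*Combined protocol and SAP*

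**What the plan says.** Under Analysis plan for primary and secondary endpoints, the change from baseline to week 4 in each endpoint "will be compared between the two treatment arms by two-sided two sample t-test or Wilcoxon rank sum test". The next sentence reads "Significance will be decided at alpha=0.05". The Statistical Methodology row of the Study Summary repeats the pair: "compared between the two treatment arms by two-sided two sample t-test or Wilcoxon rank sum test". Neither place says which test decides, on what criterion, or when the choice is made.

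The only normality condition in the section concerns descriptive summaries, which are "presented as means (SD) when they follow a normal distribution and as medians and interquartile range otherwise". A further sentence provides for log transformation of skewed variables, without a threshold.

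Baseline adjustment comes afterwards, as an addition: "We will also construct multivariable regression models with treatment assignment as the main predictor". The covariates are "characteristics such as baseline value of the endpoint, age, sex, ethnicity, hemoglobin level, and measures of disease severity", with treatment interactions if they are thought necessary. None of these models is called primary.

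**The concern.** There are two gaps, of unequal weight.

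The larger is efficiency. A comparison of change scores fixes the slope of the week-4 value on baseline at 1. ANCOVA estimates that slope, and when the true slope is below 1 its residual variance is smaller. The trial has little precision to spare. The last row of Table 2 (20% drop-out, SD 8 s) gives a detectable difference of 10.4 s, while the sample size section says "A 10-second change in phosphocreatine recovery time is likely meaningful". The baseline scan is already scheduled for every patient, so adjustment needs no extra data.

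The smaller is the open choice of test. Two p-values are available for the primary endpoint and nothing settles in advance which one counts. Blinding of allocation until database lock does not close this, because the choice could still be made after unblinding. The log provision adds another open choice, and a log cannot be taken of a change score that is zero or negative.

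**Working it through.** **Inputs from the documents.** Two-sided alpha 0.05 and power 0.90 ("assuming 0-20% dropout, power=0.90, two-tailed alpha=0.05"); 16 per arm, or 13 after 20% drop-out; SD from 2 to 8 s; a 10 s change as the meaningful size. All are in the sample size section.

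**Assumed.** The pre-post correlation r of recovery time is not given, so r = 0.3, 0.5, 0.7 and 0.9 are used. Variances are taken as equal at both visits unless stated. Table 2's SD is read as the per-patient SD of change, a reading that reproduces the table.

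**Table 2 first.** The detectable difference in SD units is (z0.975 + z0.90) × √(2/n).
- n = 16: (1.960 + 1.282) × √(2/16) = 1.146, tabulated as 1.15.
- n = 13: (1.960 + 1.282) × √(2/13) = 1.271, tabulated as 1.3.

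The table is thus a normal approximation for an unadjusted two-sample comparison. With the exact t distribution the values are 1.185 and 1.326 SD, and power at the tabulated differences is 0.88 and 0.89.

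**Variance ratio.** With a common SD S at both visits, the change score has variance 2S²(1 − r) and the ANCOVA residual has variance S²(1 − r²). The ratio is (1 − r²) / [2(1 − r)] = (1 + r)/2, that is 0.65, 0.75, 0.85 and 0.95 for the four values of r.

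**Power.** Noncentral t is used, with 2n − 2 degrees of freedom for the change score and 2n − 3 for ANCOVA, the latter averaged over chance baseline imbalance. For 10 s at SD 8 s, d = 10/8 = 1.25. With n = 13 the unadjusted noncentrality is 1.25 × √(13/2) = 3.187, the critical t on 24 df is 2.064, and power is 0.864. For ANCOVA at r = 0.5, using the mean inflation 1 + 1/(2n − 4) = 1 + 1/22, the noncentrality is 3.187 / √(0.75 × 1.045) = 3.60. The critical t on 23 df is 2.069, and power is 0.93.

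| Scenario | Unadjusted | r = 0.3 | r = 0.5 | r = 0.7 | r = 0.9 |
|---|---|---|---|---|---|
| 10 s, SD 8 s, 13 per arm | 0.86 | 0.96 | 0.93 | 0.90 | 0.86 |
| 10 s, SD 8 s, 16 per arm | 0.93 | 0.99 | 0.97 | 0.95 | 0.93 |
| 1.3 SD, 13 per arm | 0.89 | 0.97 | 0.95 | 0.92 | 0.89 |
| 1.15 SD, 16 per arm | 0.88 | 0.97 | 0.95 | 0.92 | 0.89 |
| Detectable at 90% power, SD 8 s, 13 per arm | 10.6 s | 8.8 s | 9.4 s | 10.0 s | 10.6 s |

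**Cost.** Losing one degree of freedom by itself costs about 0.1 point of power. Including the imbalance term, ANCOVA breaks even at r of about 0.93 (16 per arm) and 0.91 (13 per arm). At r = 0.98 it loses about 1 point.

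**Unequal variances** (20,000 simulated trials, 13 per arm, d = 1.25). If the week-4 SD is 20% larger than baseline, power goes from 0.862 to 0.927 (r = 0.3), 0.868 to 0.891 (0.5), 0.865 to 0.859 (0.7) and 0.863 to 0.856 (0.9). If it is 20% smaller, power rises from about 0.865 to between 0.96 and 0.99.

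**Open choice of test** (simulated, normal changes). The t-test and Wilcoxon disagree at 0.05 in about 2% of null trials and in 5 to 8% of trials with an effect of 0.8 or 1.15 SD. Taking the smaller p-value gives a type I error of 5.6 to 5.9%, and up to 6.1% with skewed or heavy-tailed data. If the baseline-adjusted model could also be picked, it is 6.7 to 8.0%. ANCOVA named alone holds 4.9 to 5.2%.

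**The case against.** The unadjusted change-score test is unbiased, it matches the endpoint as defined, and adjusted models are already planned alongside it. With baseline in the model, using change or the week-4 value as the outcome gives the same treatment coefficient, so the proposal only reorders analyses. All of this is correct. But the planned adjusted models are neither primary nor fixed, and their full covariate list would use far more than one degree of freedom in 26 to 32 patients.

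The shortfall is also confined to one of Table 2's eight cells, and 10.4 s is partly rounding (1.271 × 8 = 10.2 s, against 10.6 s by exact t). At SD 6 s and 13 per arm, unadjusted power for 10 s is already 0.98. The only SD reported is the pilot's 3.4 s, although that comes from three uncontrolled patients. The Study Design section says 36 will be randomised, not 32. With 18 per arm and 20% loss (about 14), the table's method gives 9.8 s (exact t 10.2 s). These points limit the gain. They do not reverse it.

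The size of r matters most. At a change SD of 8 s, S = 8 / √(2(1 − r)), so r = 0.3, 0.5, 0.7 and 0.9 imply a between-patient SD of 6.8, 8.0, 10.3 and 17.9 s. If S were 10 to 15 s (an assumption), r would be 0.68 to 0.86 and the gain about 1 to 4 points. The largest gains need a narrow spread between patients, which the documents neither support nor exclude.

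Finally, no calculation was done for the secondary endpoints. Mean ferritin rose from 67 to 783 ng/mL in the treated pilot patients, so equal variances are doubtful there. Fixing a log scale on the raw values in advance largely meets this.

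**Conclusion.** The concern holds. No rule selects the deciding test, and the baseline-adjusted analysis is neither primary nor fully specified. In Table 2's least favourable case, naming ANCOVA raises power for 10 s from 0.86 to between 0.86 and 0.96 as r falls from 0.9 to 0.3. The gain is negligible at an SD of 6 s or less, or at r near 0.9. Where ANCOVA loses, at very high r or with a larger week-4 variance, it loses about 1 point or less. The main figures assume normal data, equal variances at both visits, a common slope and an r that the documents do not report. The type I cost of choosing between the t-test and Wilcoxon is about 1 point. This is a matter of pre-specification and efficiency that should be corrected. It does not make the planned test invalid.

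**What to change.** Name one primary analysis in the analysis section and in the Study Summary: ANCOVA of week-4 phosphocreatine recovery time on treatment arm, with baseline recovery time as the only covariate, two-sided at 0.05, reporting the adjusted difference and its 95% CI. Use the same model for each secondary endpoint with its own baseline. State the analysis scale for each endpoint in advance, with any log applied to the raw value at each visit and not to the change. Keep the Wilcoxon test on change as a labelled sensitivity analysis, and label the multi-covariate and interaction models exploratory.

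The cost is SAP wording and one degree of freedom (30 to 29 with 16 per arm, 24 to 23 with 13). No patients, visits or measurements are added. The change should be made before unblinding.
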